## 2.4 Outcome Variables

### **Primary**

The primary outcome variable is:

- 24-hour total urinary NNAL (ng/24 hours) excreted on Day 7.

### **Secondary**

The secondary outcome variables are:

- 24-hour urinary total total NNN, NE, 2-AN, 4-ABP, HEMA, CEMA, S-PMA, 3-HMPMA, 3-HPMA, 2-HPMA, AAMA, GAMA, 2-MHBMA, 2-OHFle, 2-Naphthol, 1-OHPhe, mutagenicity, and 1-OHP excreted on Day 5 and Day 7.
- 24-hour urinary total NNAL excreted on Day 5.
- COHb on Day 5 and Day 7.
- QSU-Brief responses and factor scores on Day 1, Day 5, and Day 7.
- Responses to the appropriate mCEQ on Day 1, Day 5, and Day 7.
- Responses to the appropriate Use the Product Again questionnaire on Day 7.
- Product use behavior daily from Day 1 to Day 7 (i.e., CPD, VPD, and the average and total duration of VERVE® product use each day).

### **Clinical Safety**

[figure not shown]
- AEs and SAEs
- ECG, vital signs, clinical chemistry, urinalysis, and hematology

### **3. STUDY DESIGN**

This is an open label, randomized, 6 parallel-group clinical study evaluating changes in exposure to selected HPHCs, subjective effects, and product use behavior in adult smokers who are randomly assigned to continue smoking, partially or completely switch to VERVE® Chews or VERVE® Discs products, or stop using all tobacco products for 7 days.

The overall design of the study is shown in [Figure 1](#).

**Figure 1: Overall Study Design**

#### Study Products:

Product A:      Subject's own brand (OB) Cigarette (Reference Product)

Product B:	Oral tobacco-derived nicotine chews marketed as VERVE® Discs Blue Mint (~1.5 mg nicotine/piece) (Test Product)
Product C:	Oral tobacco-derived nicotine chews marketed as VERVE® Discs Green Mint (~1.5 mg nicotine/piece) (Test Product)
Product D:	Oral tobacco-derived nicotine chews marketed as VERVE® Chews Blue Mint (~1.5 mg nicotine/piece) (Test Product)
Product E:	Oral tobacco-derived nicotine chews marketed as VERVE® Chews Green Mint (~1.5 mg nicotine/piece) (Test Product)

Approximately 210 healthy adult male and female (no more than 60% of either gender) self-affirmed combustible cigarette smokers, 21 - 65 years of age, inclusive (determined at Screening), willing to abstain from smoking and use all four VERVE® products, and who fulfill all inclusion criteria and none of the exclusion criteria will be enrolled. All subjects must have an average daily consumption of at least 10 but no more than 30 factory manufactured combustible cigarettes for at least 12 months prior to Screening. Use of other types of tobacco- or nicotine-containing products will not be permitted within 1 week prior to Check-in.

Subjects, who meet all inclusion criteria and none of the exclusion criteria, will check-in to the clinic on Day -3 at a time determined by the clinic. After check-in, subjects will engage in a brief product trial with each flavor of VERVE® Chews (two flavors: blue mint and green mint) and VERVE® Discs (two flavors: blue mint and green mint). This trial period will involve *ad libitum* use for 10 minutes each to allow subjects to become accustomed to using the products. The trial of each flavor of VERVE® Chews or VERVE® Discs product will be separated by approximately 30 minutes (from the start of each product trial). Subjects who are unwilling to use and/or cannot tolerate all four VERVE® products will not continue in the study.

Following completion of the VERVE® product trial on Day -3, subjects will continue to smoke their OB cigarettes through 23:00 on Day -3 and from 07:00 to 23:00 on Days -2 and -1. Baseline cigarette consumption for each subject will be determined by the average number of cigarettes smoked (CPD) on Day -2 and Day -1 and will be used to calculate the CPD allowed for each subject in Group 2 or Group 3, according to their assigned randomization group, for the remainder of the study. Other baseline study events will include 24-hour urine collections for biomarkers of exposure (total NNAL, total NNN, NE, 2-AN, 4-ABP, HEMA, CEMA, S-PMA, 3-HMPMA, 3-HPMA, 2-HPMA, AAMA, GAMA, 2-MHBMA, 2-OHFle, 2-Naphthol, 1-OHPhe, mutagenicity, and 1-OHP), blood sampling for COHb, and administration of the QSU-Brief and the appropriate mCEQ questionnaire on Day -1.

On Day 1, subjects will be randomized into one of the following Groups:

- GROUP 1 (n = 40): Continue Smoking

Subjects will be asked to continue smoking their OB cigarettes *ad libitum* for 7 days.

- GROUP 2 (n = 40): VERVE® Discs Dual Use

Subjects will reduce their normal daily cigarette consumption by at least 50% of their baseline CPD and use at least 3 VERVE® Discs per day for 7 days.

- GROUP 3 (n = 40): VERVE® Chews Dual Use

Subjects will reduce their normal daily cigarette consumption by at least 50% of their baseline CPD and use at least 3 VERVE® Chews per day for 7 days.

- GROUP 4 (n = 30): VERVE® Discs Exclusive Use

Subjects will completely switch to exclusive use of VERVE® Discs, using at least 3 discs per day for 7 days.

- GROUP 5 (n = 30): VERVE® Chews Exclusive Use

Subjects will completely switch to exclusive use of VERVE® Chews, using at least 3 chews per day for 7 days.

- GROUP 6 (n = 30): Tobacco Cessation

Subjects will completely stop all tobacco product usage for 7 days.

Subjects will be randomized into each Group on Day 1 based on gender and CPD.

Subjects will begin using the assigned study products or completely stop using tobacco products on the morning of Day 1 and continue through discharge according to the randomization.

On each study day (Days 1 - 7), subjects in Group 1 will be allowed to smoke their OB cigarettes *ad libitum* (i.e., no restriction on the duration of use or the number of cigarettes per day) from 07:00 through 23:00. Subjects will be allowed to smoke upon request to the clinic staff but will only be allowed 1 cigarette at a time and will be instructed to return each cigarette butt upon completion.

On each study day (Days 1 - 7), subjects in Group 2 and Group 3 will smoke no more than 50% of their baseline CPD and will use the assigned VERVE® product *ad libitum* (i.e., no restrictions on the number of VERVE® products used at once, the number of VERVE® products used per day, or the duration of use) except for 3 specific VERVE® products use opportunities at approximately 11:00, 15:00, and 19:00 each day during which subjects will be asked to keep the assigned VERVE® product in their mouth for at least 10 minutes. Subjects will be allowed to smoke upon request to the clinic staff but will only be allowed 1 cigarette at a time and will be instructed to return each cigarette butt upon completion. Subjects will be allowed to use the VERVE® product upon request [more than 1 permitted at a time, but all returned before more are dispensed] and they will be instructed to return each used VERVE® product upon completion.

On each study day (Days 1 - 7), subjects in Group 4 and Group 5 will use the assigned VERVE® product *ad libitum* (i.e., no restrictions on the number of VERVE® products used at once, the number of VERVE® products used per day, or the duration of use) except for 3 specific VERVE® products use opportunities at approximately

11:00, 15:00, and 19:00 each day during which subjects will be asked to keep the assigned VERVE® product in their mouth for at least 10 minutes. Subjects will be allowed to use the VERVE® product upon request [more than 1 permitted at a time, but all returned before more are dispensed] and they will be instructed to return each used VERVE® product upon completion.

On each study day (Days 1 - 7), subjects in Group 6 will completely stop cigarette use and they will not be allowed to smoke or use VERVE® products.

All product use (CPD, VPD, and VERVE® product use duration, [i.e., time of VERVE® product placement in the subjects' mouth, and time it was removed from the subjects' mouth], as appropriate) will be determined to assess product use behavior.

Study events will include 24-hour urine collections for biomarkers of exposure (total NNAL, total NNN, NE, 2-AN, 4-ABP, HEMA, CEMA, S-PMA, 3-HMPMA, 3-HPMA, 2-HPMA, AAMA, GAMA, 2-MHBMA, 2-OHFle, 2-Naphthol, 1-OHPhe, mutagenicity, and 1-OHP) and blood sample collection for COHb assessment. Urine creatinine will be measured in each 24-hour collection and will be used to adjust the concentration values of urine biomarkers. Each 24-hour urine collection (Day -1, Day 5 and Day 7) will be from approximately ( $\pm$  30 minutes) 07:00 on the scheduled day to approximately 07:00 the following day. The 24-hour urine collection begins on each scheduled day after the first morning void and any void prior to 07:00, and finishes the following morning with the last void collected at approximately 07:00 (including first morning void). Subjects will be specifically instructed to collect all urine voided, and any missed collection during the 24-hour interval will be documented as a deviation.

Subjects will also complete in the moment subjective effects questionnaires, which include QSU-Brief (Protocol Appendix 2), Modified Cigarette Evaluation Questionnaire (mCEQ-C & mCEQ-V; Protocol Appendix 3), and Use the Product Again questionnaire (UPA-C & UPA-V; Protocol Appendix 4). Details for subject effect data collection is in Section 7.1.4.1.

#### 4. SAMPLE SIZE ESTIMATION

This study is designed to evaluate changes in exposure to selected HPHC when adult smokers partially or completely switch to oral tobacco-derived nicotine VERVE® Chews or VERVE® Discs compared to those who continue smoking cigarettes or stop using all tobacco products. Assuming a similar effect size for the new study as for the previous ALCS study (ToPP4ST\_1011\_07) between the continued cigarette smoking group and each of the two dual usage groups ( $\geq 50\%$  CPD reduction with VERVE® DISCS or VERVE® CHEWS), a two-sided t test, 85% power and an  $\alpha = 0.025$  Type I error rate to account for the multiplicity adjustment for the two comparisons, 35 subjects are needed to complete for the continue cigarette smoking group and the dual usage groups. We expect that the effect will be larger in the VERVE® only and smoking cessation groups, so 25 subjects are needed to complete in these groups.

## 5. ANALYSIS POPULATIONS

### **Safety Analysis Dataset:**

All subjects who used any study products (including subjects randomized to Group 6).

### **Modified Intent-to-Treat (mITT) Dataset:**

All randomized subjects who used at least one study product after randomization (except Group 6) and have a valid baseline and at least one post-baseline biomarker measure of any one biomarker.

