**Figure 1: Overall Study Design**

#### Study Products:

Product A: Subject's OB Cigarette (Reference Product)

Product B: Oral tobacco-derived nicotine chews marketed as VERVE® Discs Blue Mint (~1.5 mg nicotine/piece) (Test Product)

Product C: Oral tobacco-derived nicotine chews marketed as VERVE® Discs Green Mint (~1.5 mg nicotine/piece) (Test Product)

Product D: Oral tobacco-derived nicotine chews marketed as VERVE® Chews Blue Mint (~1.5 mg nicotine/piece) (Test Product)

Product E: Oral tobacco-derived nicotine chews marketed as VERVE® Chews Green Mint (~1.5 mg nicotine/piece) (Test Product)

This study will enroll healthy adult male and female (no more than 60% of either gender) self-affirmed combustible cigarette smokers, 21 - 65 years of age, inclusive (determined at Screening), willing to abstain from smoking and use all four VERVE® products, and who fulfill all inclusion criteria and none of the exclusion criteria. Approximately 210 subjects will be enrolled to the study. All subjects must have an average daily consumption of at least 10 but no more than 30 factory manufactured combustible cigarettes for at least 12 months prior to Screening. Use of other types of tobacco- or nicotine-containing products will not be permitted within 1 week prior to Check-in.

Subjects will not be forced to smoke or use any tobacco product at any time during the study.

Subjects, who meet all inclusion criteria and none of the exclusion criteria, will check-in to the clinic on Day -3 at a time determined by the clinic. After check-in, subjects will engage in a brief product trial with each flavor of VERVE® Chews (two flavors: blue mint and green mint) and VERVE® Discs (two flavors: blue mint and green mint). This trial period will involve *ad libitum* use for 10 minutes each to allow subjects to become accustomed to using the products. The trial of each flavor of VERVE® Chews or VERVE® Discs product will be separated by approximately 30 minutes (from the start of each product trial). Subjects who are unwilling to use and/or cannot tolerate all four VERVE® products will not continue in the study.

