### Modified Intent-to-Treat (MITT) Dataset:

All randomized subjects who have a valid baseline and post-baseline endpoint value (total NNAL). This population will be used for primary endpoints analysis.

Per-Protocol (PP) Dataset:

A subset of the MITT dataset and includes subjects who completed the study without major protocol deviations that are considered to impact data integrity (e.g., non-adherence to study group assignment).

If it is determined that a subject was pregnant during the study, all of the pregnant subject's data will be reported, but will be excluded from summarization and statistical analyses.

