## 7.3 Statistical Analyses

### 7.3.1 Primary Endpoint Analysis

A linear mixed model for repeated measures (MMRM) analysis will be used for comparing each test group (Groups 2-5) to the control group (Group 1 and Group 6) in the primary endpoint (24-hour total urinary NNAL (mg/24 hours) excreted on Day 7). In the model, study group, study day, and study group by study day interaction, and gender are the fixed effect factors. The baseline value of the response biomarker is the covariate. A restricted maximum likelihood estimation method will be applied and several covariance structures will be tried. Five candidate covariance structures will be considered: compound symmetry, 1st order autoregressive, 1st order autoregressive with a random subject effect, unstructured and Toeplitz. The most appropriate covariance structure will be determined based on the AIC criteria (the covariance structure with the smallest AIC will be chosen). The least-square mean, 95% confidence interval and p-value will be provided for the study groups. The least-square mean difference, 95% confidence interval and p-value will be provided for the study group comparisons. Pairwise comparisons (Group 2 vs. Group 1, Group 3 vs. Group 1, Group 4 vs. Group 1, Group 5 vs. Group 1, Group 2 vs. Group 6, Group 3 vs. Group 6, Group 4 vs. Group 6, and Group 5 vs. Group 6,) will be performed using a Dunnett's test at a 2-sided significance level of 0.05 to adjust for multiplicity. Group 1 & 6 will be considered as the control groups. The test is for each of the other groups to compare with the control groups. The analysis will be conducted on the mITT and PP datasets.

The following SAS codes will be used to perform the analysis.

```
Proc mixed data=<>;
Class subject gender group day;
Model response = gender group day group*day baseline/ddfm=kr;
Repeated day/type=<type> subject=subject;
LSmeans group*day/CL alpha=0.05 pdiff dunnett ('1'*Day 7, '6'*Day 7);
```

Run;

Note: This model will include both the Day 7 value (primary endpoint) and interim time points (Day 5, secondary endpoint). The above analysis will also output the residual diagnosis to check for normality and to identify outliers).

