# **9. SUMMARY OF CHANGES FROM PROTOCOL-PLANNED ANALYSIS**

The analyses described in this SAP are aligned with those analyses described in the protocol with the following changes for statistical analysis.

1. Mixed model with repeated measurement instead of mixed model will be used in the analysis for biomarker statistical analysis as there are two response values (Days 5 and 7) for each subject.
2. Emax for Use Product Again questionnaire was mentioned in the protocol. As the Use Product Again questionnaire will only be conducted at Day 7 and only one response value for each subject, no maximum value will be available. The analysis will be performed based on the original response.
3. The statistical analysis model for Use Product Again questionnaire was modified based on the study design and data collection.

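### SAP Section 5 makes mITT depend on post-randomisation product use (Groups 1-5 only) and on any one biomarker instead of NNAL, and SAP Section 9 lists neither change; the numerical effect should be small

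*SAP*

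**What the plan says.** **Protocol 11.3** defines the set as "All randomized subjects who have a valid baseline and post-baseline endpoint value (total NNAL" being the endpoint in question. It adds: "This population will be used for primary endpoints analysis". Product use plays no part.

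**SAP Section 5** uses the same name with two different conditions. A subject must have "used at least one study product after randomization (except Group 6" being the one exempt arm. The data condition becomes a valid baseline and "at least one post-baseline biomarker measure of any one biomarker". PP is defined as a subset of this set.

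**SAP 7.3.1** says of the primary endpoint: "The analysis will be conducted on the mITT and PP datasets". It does not say which of the two is primary.

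**SAP Section 9** opens with "The analyses described in this SAP are aligned with those analyses described in the protocol with the following changes for statistical analysis". It then lists three items: the repeated-measures model, the dropping of Emax for the Use the Product Again questionnaire, and a modified model for that questionnaire. Populations are not mentioned.

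**Protocol 3.1** makes use voluntary: "Subjects will not be forced to smoke or use any tobacco product at any time during the study". Protocol 1.1.4 and 6.1 count own-brand cigarettes as a study product (Product A).

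**The concern.** An intention-to-treat type of set is meant to be fixed by randomisation and, in a modified form, by the availability of data. The SAP adds a test of behaviour after randomisation and applies it in five arms out of six. A Group 4 or 5 subject who uses nothing is removed, while a subject who behaves identically in Group 6 stays. Group 6 is the control in four of the eight comparisons in SAP 7.3.1. Adherence already has its own set, PP.

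The second change loosens the tie between the set and the endpoint. SAP 7.3.4.2 bases the trigger for imputation on the proportion missing in mITT and expects no missing baselines there. Under the protocol's definition an NNAL baseline is present by construction; under the SAP's it is not.

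Both changes are undeclared, so a reader of SAP Section 9 would take the primary set to be the protocol's.

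**Working it through.** **1. Whom the use clause removes.** Urine biomarkers and COHb are measured after baseline only on Days 5 and 7 (Protocol 7.7 and 7.8; SAP 7.1.1.1 and 7.1.2.1). Early termination calls for safety data only (Protocol Section 9). A subject who leaves before using any product therefore has no post-baseline biomarker and already fails the SAP's data condition. Those removed by the use clause alone stayed, gave a Day 5 or Day 7 sample, and used no study product.

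**2. The two definitions side by side.**

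| Subject | Protocol MITT | SAP mITT | In the SAP's NNAL model? |
|---|---|---|---|
| Group 2 or 3, smoked, no VERVE, full NNAL data | in | in | yes |
| Groups 1-5, no study product at all, full NNAL data | in | **out** | **no** |
| Group 6, abstinent, full NNAL data | in | in | yes |
| Any group, NNAL at baseline, only COHb afterwards (Group 6 or a product user) | out | **in** | no (no response) |
| Any group, no NNAL baseline, another biomarker at baseline (Group 6 or a product user) | out | **in** | no (no covariate) |

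The second row is where the primary estimate can differ. The last two rows do not change that estimate, because the model needs an NNAL response and an NNAL baseline.

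**3. Likelihood of non-use.** Groups 2-5 have 3 scheduled VERVE opportunities a day, so 3 × 7 = 21 over Days 1-7. Exclusion requires using nothing at any of them and nothing between them. In Groups 1-3 it also requires taking no cigarette for the week. No expected number of non-users is given.

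**4. Size, by assumption only.** Suppose *k* of *n* subjects in an arm are non-users whose mean NNAL is *r* times the users' mean. Dropping them multiplies the arm mean by 1 / [1 − (k/n)(1 − r)]. Neither *k* nor *r* is in the documents.

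| n | k | r = 1 | r = 0.5 |
|---|---|---|---|
| 30 | 1 | 0% | 1/(1 − 0.0167) = +1.7% |
| 30 | 2 | 0% | 1/(1 − 0.0333) = +3.4% |
| 40 | 1 | 0% | 1/(1 − 0.0125) = +1.3% |
| 40 | 2 | 0% | 1/(1 − 0.025) = +2.6% |

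On the SD scale the shift is (k/n) × δ, where δ is the difference between excluded and retained subjects. With k = 1 to 4 and δ = 0.5 to 2 SD (assumed), it is 0.01 to 0.20 SD for n = 40 and 0.02 to 0.27 SD for n = 30.

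The direction depends on the arm. If non-users have lower NNAL, dropping them from Groups 2-5 raises the test mean, which works against showing a reduction versus Group 1. Dropping them from Group 1 raises the reference mean, which works in favour.

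**5. Power.** The planned 35 completers per group cannot be reproduced, because the effect size is taken from an earlier sponsor study and not stated. Solving backwards (two-sided t test, α = 0.025, 85% power) gives a standardised difference of 0.80. At that value, power is 89.8% with 40 versus 40 and 89.0% with 40 versus 38. Losing one or two subjects is not a power problem.

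**6. Missing-data trigger.** The planned total is 3 × 40 + 3 × 30 = 210, and 5% of that is 10.5. If all were in mITT, 11 missing Day 7 values would start the imputation analyses. Each subject admitted on another biomarker without Day 7 NNAL adds one to both numerator and denominator. For example, 10/209 = 4.8% becomes 11/210 = 5.2%. A subject with only a baseline NNAL could also have that value carried forward to Day 7, since SAP 7.3.4.2 does not say whether baseline may be the last observation.

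**The case against.** The best defence is that almost nobody meets the exclusion. These are smokers of 10-30 cigarettes a day with no plan to quit, confined, and willing to use all four VERVE products after a trial. The clause asks for any study product, so a dual-use subject who only smoked stays in. That stands, and it keeps the point small. A reader might infer that everyone who avoided VERVE in Groups 2-5 is dropped, or that the primary comparison is materially biased. The documents support neither reading.

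A percentage bias is also tempting, but nothing in the documents says how NNAL differs between VERVE users and non-users. At a ratio of 1 the shift is zero.

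It is fair, too, that one common set serves COHb, product use and questionnaires, and that an NNAL-only set would discard valid COHb data. The wider wording may even be an improvement: if the protocol's endpoint value means Day 7 NNAL, its MITT leaves no missing Day 7 value for SAP 7.3.4.2 to impute. This argues for a rule per biomarker. It does not argue for the use clause.

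The SAP only says that a missing baseline is not expected, and all urine analytes come from one pooled collection. So the statement is no longer guaranteed by definition, but it has not been shown to be wrong.

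A reader might also infer that two sets are being kept to choose between once open-label data are seen. The protocol defers statistical detail to the SAP, the SAP defines a single mITT, and planned listings show each subject's populations and the exclusions. No such intent is supported. What remains is that the change is undeclared.

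Group 6 has no assigned product, so it needs an exemption if a use condition is kept. Without the condition, no exemption is needed.

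**Conclusion.** The point holds as a discrepancy between documents and an unnecessary exclusion rule. SAP Section 5 departs from Protocol 11.3 in two ways that SAP Section 9 does not declare. The use clause can only discard randomised subjects with observed post-baseline biomarker data because of their behaviour after randomisation. Since PP sits inside mITT, no planned biomarker analysis keeps them.

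The expected numerical effect is small, and probably near zero for the primary comparison of Groups 2 and 3 with Group 1. This rests on total non-use being rare in confinement, which is a judgement. The percentages and SD shifts above are illustrations on assumed inputs and not estimates for this trial.

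The any-biomarker wording has little effect on the primary mixed model. It does alter the mITT denominator, the 5% trigger and who is imputed, and it removes the guarantee of an NNAL baseline.

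**What to change.** - **SAP Section 5:** delete the product-use condition and the Group 6 exemption with it. For each biomarker analysis, use all randomised subjects with a valid baseline and at least one post-baseline value of that biomarker, analysed as randomised. For NNAL, let a Day 5 or a Day 7 value qualify, so that the Day 7 missing-data analyses in SAP 7.3.4.2 still have a purpose.
- **SAP 7.3.1:** state that mITT is the primary set, as the protocol does, and leave adherence to PP.
- **SAP Section 9:** record any remaining difference from Protocol 11.3, including the Day 5 or Day 7 rule.

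If the sponsor keeps the use clause, the least that is needed is to list and justify it in SAP Section 9 and to report the protocol-defined set as a sensitivity analysis.

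The cost is one paragraph in SAP Section 5 and a sentence each in SAP 7.3.1 and Section 9, with no new data. It should be settled before database lock.
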